4.3 Safety Outcomes

The safety and tolerability of intravitreal ranibizumab have been investigated in previous Phase I, I/II and III studies in AMD, RVO, and DME trials. Potential safety issues associated with the route of administration or the pharmacology of aflibercept in the study population include decreased BCVA, intraocular inflammation, intraocular infection, transient and/or sustained elevation of intraocular pressure (IOP), cataract development or progression, retinal or intraretinal hemorrhage, macular edema, retinal break or detachment, and arterial thromboembolic events (ATEs). Safety will be assessed by visual acuity, ophthalmic examinations, fluorescein angiograms, SD-OCT, intraocular pressure, vital signs, and adverse event documentation.

To minimize the risks of intraocular infections, all injections will be performed employing sterile techniques. Study drug administration will be held for subjects who experience certain ocular events or infections. In the event any subject develops an adverse event in the study eye that is considered by the evaluating physician to be severe in intensity, serious consideration should be given to withdrawing the subject from the study.

The PI or designated Sub-Investigators will review all adverse events on an ongoing basis to determine causality and relationship to study drug and/or study procedures.

5. POPULATIONS

Subjects were eligible to participate if the following criteria were met:

A subject must meet the following criteria to be eligible for inclusion in the study:

- 1. Ability to provide written informed consent and comply with study assessments for the full duration of the study
- 2. Age ≥18 years
- 3. Active radiation retinopathy resulting from any form of radiation treatment. Radiation retinopathy is defined as any of the following: retinal hemorrhages, exudates, edema, and/or neovascularization, not attributable to other causes
- 4. BCVA of 20/25 to 20/400 in the study eye

A subject who meets any of the following criteria will be excluded from the study:

- 1. Pregnancy (verified by positive pregnancy test) or lactation
- 2. Premenopausal women not using adequate methods of contraception
- 3. Any other condition that the investigator believes would pos a significant hazard to the subject if the investigational therapy were initiated
- 4. Participation in any other simultaneous medical investigation or trial
- 5. Previous participation in any studies involving investigational drugs within 30 days before Day 0 (excluding vitamins and minerals)
- 6. History of allergy fluorescein, not amenable to treatment
- 7. Previous intravitreal treatment with any anti-VEGF drug within 60 days of Day 0
- 8. Previous intravitreal or subconjunctival treatment with cortical steroids within 90 days of Day 0

- 9. History of vitrectomy
- 10. History of treatment with more than one form of radiation to the eye
- 11. Subjects who have more than 7DD of ischemia in the central macula that would hinder visual acuity improvement
- 12. History of panretinal photocoagulation treatment in the study eye
- 13. Inability to obtain fundus photographs or fluorescein angiograms of sufficient quality to be analyzed
- 14. Any concurrent intraocular condition in the study eye that, in the opinion of the investigator, could:
 - a. Require medical or surgical intervention during the 104 week study period to prevent or treat visual loss that might result from that condition
 - b. Contribute to loss of at least 2 Snellen equivalent lines of BCVA over the 104 week study period, if allowed to progress untreated
- 15. Active intraocular inflammation (grade 2+ or above) in the study eye
- 16. Current vitreous hemorrhage in the study eye
- 17. History of rhegmatogenous retinal detachment or macular hole (stage 3 or 4) in the study eye
- 18. Active infectious or conjunctivitis, keratitis, scleritis, or endophthalmitis in either eye
- 19. Aphakia or absence of the posterior capsule in the study eye
- 20. Intraocular surgery (including cataract surgery) in the study eye within 2 months preceding Day 0
- 21. Uncontrolled glaucoma in the study eye (defined as $IOP \ge 30$ mmHg despite treatment with anti-glaucoma medication)
- 22. History of glaucoma-filtering surgery in the study eye
- 23. History of corneal transplant in the study eye
- 24. Uncontrolled blood pressure (defined as systolic and/or diastolic >180/110 mmHg while subject is seated). A second reading may be taken at least 30 minutes later. If the subject requires antihypertensive medication, the subject can become eligible if medication is taken continuously for at least 14 days prior to Day 0 and blood pressure is less than 180/110 mmHg
- 25. New diagnosis of atrial fibrillation not managed by subject's primary care physician or cardiologist within 3 months of Day 0
- 26. History of stroke within the last 3 months of Day 0
- 27. History of myocardial infarction within 3 months of Day 0
- 28. History of other disease, metabolic dysfunction, or physical examination finding giving reasonable suspicion of a disease or condition that contraindicates the use of an investigational drug or that might affect interpretation of the results of the study or renders the subject at high risk for treatment complications
- 29. Active malignancy other than uveal melanoma
- 30. Presence of metastases

6. ANALYSES

All outcomes will be presented using descriptive statistics. For comparison of groups for primary and secondary outcomes, variables of interest will be statistically analyzed using analysis of variance (ANOVA), Student's t-tests, Chi square and Fisher's exact test. ETDRS data will be obtained for all visits

for all 40 of the participants. Bonferroni correction was applied to all pairwise comparison analyses for this study.

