2. OVERVIEW OF STUDY DESIGN

This trial will compare the results of 3 different combinations of therapy to assess the efficacy of peripheral targeted retinal photocoagulation (TRP) applied to areas of retinal nonperfusion and poor perfusion combined with ranibizumab injections for the treatment of macular edema secondary to radiation retinopathy. Specifically, this trial will evaluate the ability to reduce the monthly treatment burden by eliminating areas of peripheral ischemia as detected by wide field fluorescein angiography. This peripheral ischemic retina is likely a major VEGF production site. By selectively eliminating these ischemic areas with angiography-guided laser ablation while preserving more perfused areas of peripheral retinal, pathological levels of VEGF may be significantly reduced, translating into fewer necessary monthly intravitreal injections while preserving useful peripheral visual field. The study will include 3 cohorts followed for a total of 104 weeks.

Subjects will be randomized into one of three treatment cohorts in a 1:2:2 ratio.

Day 1 through Week 48:

- Cohort A (n=8) will receive monthly treatment of 0.5 mg ranibizumab for 48 weeks. Monthly treatment is defined as every 28 days (+/- 7 days).
- Cohort B (n=16) will receive monthly treatment of 0.5mg ranibizumab for 48 weeks. 1 week (+/-3 days) after the initial dose of ranibizumab is delivered, the subject will have peripheral targeted-retinal photocoagulation (TRP) to areas of peripheral retinal ischemia based on wide field angiography that was performed at the screen visit. After the first session of TRP, subjects will have a repeat wide field angiogram at week 24 and week 36 and will receive additional TRP as needed (PRN) to areas of peripheral retinal ischemia.
- Cohort C (n=16) will receive a loading dose (3 consecutive monthly doses) of 0.5mg ranibizumab followed by PRN treatment with 0.5mg ranibizumab. 1 week (+/- 3 days) after the initial dose of ranibizumab is delivered, the subject will have peripheral TRP to areas of peripheral retinal ischemia based on wide field angiography that was performed at the screen visit. After the first session of TRP, subjects will have a repeat wide field angiogram at week 24 and week 36 and will receive additional TRP as needed to areas of peripheral retinal ischemia.

See RRR protocol for TRP and PRN treatment criteria.

Week 52 through Week 101:

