2.1 Sample Size Calculations

A priori power calculation was performed and revealed that a sample size of n=41 was needed to achieve 80% power using single factor ANOVA with a significance level (alpha) of 0.05. Based on this result, the final study size was 40. Patients randomized in a 1:2:2 ratio. Sample size estimation was performed using RStudio (Version 1.1.463, RStudio Inc., Boston, Massachusetts). Statistical analyses were performed using Prism (GraftPad Software, San Diego, CA) and the data analysis function in Microsoft Excel (Microsoft Inc., Redmond, WA).

The reason for the 1:2:2 randomization ratio was that the monthly group would have less variability in terms of treatment course because each patient would receive an injection each month without alterations or additional factors to their treatment regimen, allowing for detection of the group's trend with a smaller cohort size. On the other hand, the other two cohorts could have different treatment schedules and therefore would require more patients to capture the trend. The exception to this randomization was that patients whose central vision of 20/50 or better at screening exam were randomized into the three cohorts in a 1:1:1 ratio in order to minimize a disproportionate population of subjects with good vision in any one group and to minimize the chance of significant difference in baseline vision between groups. Randomization occurred on Day 0 in which a randomly selected envelope containing a cohort assignment was chosen for each patient.

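### Bonferroni on the three pairwise cohort comparisons is valid but conservative: with three cohorts, an omnibus gate followed by pairwise tests at the same alpha controls the same error per time point with more power

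*SAP*

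**What the plan says.** SAP section 6 lists ANOVA, Student's t-tests, chi-square and Fisher's exact test for comparing the cohorts, and adds that "Bonferroni correction was applied to all pairwise comparison analyses for this study". It does not give the divisor, does not say whether a significant ANOVA is required before pairwise testing, and does not say how weeks 48 and 104 are handled together. SAP section 6.1 compares cohorts A, B and C on mean change in ETDRS acuity at both times. Protocol section 4.8 adds no test and no multiplicity rule.

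The sample size in SAP section 2.1 rests on the omnibus test alone: "a sample size of n=41 was needed to achieve 80% power using single factor ANOVA with a significance level (alpha) of 0.05". It continues: "Based on this result, the final study size was 40". No effect size, SD or pairwise power is given. The planned groups are 8, 16 and 16.

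**The concern.** The omnibus ANOVA can say only that the cohorts differ somewhere. Which cohort differs (with or without laser, monthly or as-needed dosing) is read from the pairwise tests. Under Bonferroni with three pairs, each of these runs at 0.05/3 = 0.0167, a level for which the trial was not sized. If the same familywise protection is available at a less strict pairwise level, a 40-patient trial with 8 patients in one cohort gives up power for nothing.

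**Working it through.** **Error rate for one outcome at one time point.** Take the rule: F test at 0.05, then, only if significant, each pair at 0.05. There are three cases.

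- All three means equal: any false rejection must first pass the F test, so the chance is at most 5%.
- One cohort differs: only one true pairwise null remains, and it is tested at 5%.
- All three differ: no false rejection is possible.

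The argument is specific to three groups. Simulation at 8/16/16 with normal data and equal SDs agrees. The gated rule gives at most 5.0% within simulation error. Bonferroni with divisor 3 gives 4.3 to 4.4% when all means are equal and 1.7% when one cohort is shifted.

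**The SAP's sample size.** The figure of 41 cannot be reproduced independently, because no effect size is given. It can be inverted. With the noncentral F distribution, three groups and noncentrality N·f², 80% power at N = 41 gives f = 0.5045. A planned f of 0.50 would have given N = 42.

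**Shift in SD units.** At 8/16/16 the noncentrality is Σnᵢ(μᵢ − μ̄)², set equal to 40 × 0.5045² = 10.18.

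- Only A differs by d: (8 × 32/40)d² = 6.4d², so d = √(10.18/6.4) = 1.26.
- Only B (or only C) differs: (16 × 24/40)d² = 9.6d², so d = √(10.18/9.6) = 1.03.

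Omnibus power at N = 40 is then 79%.

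**Pairwise power** (two-sided two-sample Student's t, 200,000 simulated trials per pattern):

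| True pattern | Pair | Bonferroni, 0.05/3 | Gated, 0.05 | Gain (points) |
|---|---|---|---|---|
| Only A differs | A–B | 63% | 73% | about 10 |
| Only B differs | A–B | 43% | 59% | about 16 |
| Only B differs | B–C | 65% | 74% | about 9 |

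With shifts set for exactly 80% omnibus power (1.28 and 1.04 SD), the gains are 9.2 to 16.2 points.

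**Dependence on the effect.** With pooled error the gain is about 8 to 11 points at 50% omnibus power and 7 to 16 at 90%. For a 0.5 SD shift of one cohort it is about 4 to 5 points, and power stays below 20% either way. For example, A–B goes from about 9% to 13% when only A differs.

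**Two time points.** The 5% holds per time point. Two independent time points give 1 − 0.95² = 9.75%. Simulation over correlations of 0 to 0.8 with all means equal gives 8 to 10% for the gate at 0.05, 7 to 8% for Bonferroni/3 and 3.6 to 4.4% for Bonferroni/6. With A far from the others, it is 8 to 10% for the gate against about 3% for Bonferroni/3. A gate at 0.025 per time point caps the total at 2 × 0.025 = 0.05. Against Bonferroni/6 it still gains 9 to 14 points (A–B: 52% to 62% if only A differs, 33% to 47% if only B differs).

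**Unequal SDs.** If A's SD is 0.5 to 0.75 of the others and the pooled ANOVA error is used, the B–C test runs at 6 to 7% when A differs; two-sample t-tests stay at 5.0%. If A's SD is 1.4 times the others, the equal-variance versions reach about 8% with all means equal and about 8 to 9% for A–C when B is far away. Welch at both steps stays at about 5%.

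**Cost of Welch.** The table uses Student's t, which the SAP names. The same equal-SD runs with Welch at both steps give 70%, 56% and 71% for the three rows. That is 3 to 4 points below the gated Student figures, but 70 − 63 = 7, 56 − 43 = 13 and 71 − 65 = 6 points above Student's t with Bonferroni.

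**The case against.** The strongest reply is that the plan contains no error. Bonferroni is valid, easy to explain and compatible with simultaneous intervals. A reader might infer that the pairwise contrasts fall short of a required power, but the documents set no power target for any pair, so no shortfall can be claimed.

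A reader might also infer that Bonferroni buys nothing at all. That is too strong. Its slack limits error across the two visits and when SDs differ. If the unstated divisor was six, it controls weeks 48 and 104 jointly, and a gate at 0.05 per visit would remove that control. This part of the objection stands, and it is why alpha has to match the family that Bonferroni was meant to cover.

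Third, a gain of 9 to 16 points might be read as a fixed property of the design. It depends on an effect size that the SAP does not state, and for a modest shift it is small.

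Finally, SAP sections 2.1 and 6 are partly in the past tense. Relaxing a multiplicity rule after results are known would not be credible. What survives is narrower: at a matched alpha, and with Welch tests, the gated rule gives more power at the same nominal error.

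**Conclusion.** The point holds as an efficiency improvement. Per outcome and time point, the gated rule has the same nominal 5% familywise error as Bonferroni over three pairs. Its gain of about 9 to 16 points for a one-cohort difference (Student's t on both sides) assumes f of about 0.50, normal data with equal SDs, two-sided tests, a divisor of three and the planned 8/16/16 split. The 1:1:1 allocation of patients with vision of 20/50 or better could change that split. The gain falls to about 4 to 5 points at 0.5 SD.

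The documents do not support calling Bonferroni wrong, or claiming 5% control across both visits for a gate at 0.05. Categorical outcomes were not computed and are outside this conclusion.

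**What to change.** Replace the Bonferroni sentence in SAP section 6 with:

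> At each time point the three cohorts are compared by Welch's ANOVA; only if it is significant are the three pairwise Welch t-tests made, each at the same alpha.

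State that alpha: 0.05 per time point if Bonferroni was meant to cover three pairs at each time point, or 0.025 per time point if it was meant to cover weeks 48 and 104 together. Welch is needed at both steps because SAP section 2.1 expects treatment course to vary less in the monthly-only cohort. That says nothing certain about outcome SDs, but equal SDs cannot be taken for granted with groups of 8 and 16.

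Fix the rule before outcome data are seen. If that is no longer possible, keep Bonferroni and report the gated analysis as a sensitivity analysis.

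The cost is a short SAP edit, a few points of power for Welch if the SDs are in fact equal, and the loss of simultaneous pairwise confidence intervals, which must be labelled accordingly. No patients are added. If the sponsor prefers Bonferroni, the divisor should still be stated.

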6.1 Primary Outcome

The primary analysis will compare cohorts (A vs. B vs. C) on their mean change in ETDRS BCVA from baseline to week 48 and week 104 with the above described statistical tests. Adverse events will be reported using counts and percentages for each cohort.

6.2 Secondary Outcomes

The secondary analysis will compare cohorts (A vs. B vs. C) on their mean CMT measurements at baseline, week 48 and week 104. The secondary analysis will also compare percentage of eyes with intraretinal exudates, retinal hemorrhage, and neovascularization at baseline, week 48 and week 104. The frequency of injection will be compared between cohorts and the correlation between injection frequency and CMT and/or ETDRS BCVA will be assessed.

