4.8.4. Missing Data

Analyses of efficacy and safety will be based on available cases, without imputation for missing values.

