4.2 Secondary Outcomes

• The mean number of intravitreal injections required per subject per cohort.

- Percentage of subjects with persistent macular edema, based on SD-OCT, at week 48 and week 104 compared to day 0.
- Percentage of subjects avoiding the development of neovascular glaucoma and/or vitreous hemorrhage.

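### SAP 6.2 does not follow the secondary outcomes in SAP 4.2: two of three have no outcome-specific analysis, unlisted measures are called secondary, and CMT is compared without using its Day 0 value

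*SAP*

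**What the plan says.** Besides the number of injections per subject, SAP 4.2 lists "Percentage of subjects with persistent macular edema, based on SD-OCT, at week 48 and week 104 compared to day 0" and "Percentage of subjects avoiding the development of neovascular glaucoma and/or vitreous hemorrhage". Protocol 4.8.3.2 has the same three items. SAP 3.2 adds that injections are to be looked at as laser against non-laser.

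The section of the SAP that should analyse these outcomes, 6.2, says "The secondary analysis will compare cohorts (A vs. B vs. C) on their mean CMT measurements at baseline, week 48 and week 104", then "The secondary analysis will also compare percentage of eyes with intraretinal exudates, retinal hemorrhage, and neovascularization at baseline, week 48 and week 104". It ends with a comparison of injection frequency between cohorts and correlations of that frequency with CMT and visual acuity.

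The general text in SAP 6 promises descriptive statistics for every outcome and adds: "For comparison of groups for primary and secondary outcomes, variables of interest will be statistically analyzed using analysis of variance (ANOVA", followed by t-tests, Chi square and Fisher's exact test. On multiplicity it says "Bonferroni correction was applied to all pairwise comparison analyses for this study". Protocol 4.8.4 says "Analyses of efficacy and safety will be based on available cases, without imputation for missing values".

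**The concern.** A reader who goes from SAP 4.2 to SAP 6.2 finds one of three listed outcomes and several that were never listed. Two things are at stake. First, the unlisted measures would carry the label of secondary results, while choices that define two of the listed ones (who is in the denominator, over what period, how early leavers count) stay open and could be settled after the data are known. Second, CMT is set up as a comparison of means at each visit, whereas the primary outcome in SAP 6.1 is "mean change in ETDRS BCVA from baseline to week 48 and week 104". With planned cohorts of 8, 16 and 16, leaving a recorded Day 0 value unused gives away precision that is already scarce.

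**Working it through.** **Listed outcomes, traced forward from SAP 4.2**

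| Outcome | In SAP 6.2? | Supplied elsewhere | Left open |
|---|---|---|---|
| Injections | Yes, by cohort | Test list in SAP 6 | Early leavers; the laser contrast of SAP 3.2 |
| Persistent edema | No | Weeks 48 and 104 (SAP 3.2, 4.2); in effect Chi square or Fisher (SAP 6) | Denominator; analysis definition of edema |
| Avoiding neovascular glaucoma/vitreous hemorrhage | No | In effect Chi square or Fisher (SAP 6) | Time point; early leavers |

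So 1 of 3 listed outcomes is named.

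**SAP 6.2, traced back**

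CMT, exudates, retinal hemorrhage and neovascularization (4 measures), plus the correlations, are not in SAP 4.2. The nearest protocol endpoint to CMT is foveal thickness, which 4.8.3.3 ranks as additional and defines as a change from Day 0. Appendix D records two thicknesses, foveal and mean central subfield, and the SAP does not say which one CMT is.

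**Edema denominator**

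Protocol 4.1.2 accepts hemorrhages, exudates, edema or neovascularization, so an eye can enter without edema. A percentage of subjects points to all available subjects; persistence relative to Day 0 points to eyes that had edema then. Illustration only, with Day 0 edema in 60-90% of eyes, half of these persisting, and no new edema counted (all assumed):
- among eyes with Day 0 edema: 50%
- among all subjects: 0.6 × 0.5 = 30%, up to 0.9 × 0.5 = 45%
- gap: 20 down to 5 points, and zero if every eye has edema at Day 0.

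**Neovascular glaucoma/vitreous hemorrhage and early leavers**

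Illustration only, for a cohort of 16 with 2 events and 2-4 early leavers without an event (all assumed):
- leavers counted as avoiding: 14/16 = 87.5%
- 2 leavers excluded: 12/14 = 85.7%
- 4 leavers excluded: 10/12 = 83.3%
- shift: about 2-4 points.

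**Precision of CMT**

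Inputs: planned cohort sizes 8 and 16 (SAP 2); Day 0 to follow-up correlation r not given, so assumed at 0.3-0.7; equal SDs.
- SE of a chance Day 0 difference, A versus B: √(1/8 + 1/16) = 0.433 SD
- SE of adjusted over raw comparison = √(1 − r²): √0.91 = 0.954 at r = 0.3 and √0.51 = 0.714 at r = 0.7, a reduction of about 5% to 29%
- SE of unadjusted change over raw = √(2(1 − r)): √1.4 = 1.183 at r = 0.3 and √0.6 = 0.775 at r = 0.7.

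The gain is therefore assured only for the baseline-adjusted comparison; a plain change score is worse than raw means when r is below 0.5. These ratios ignore the small loss of degrees of freedom from adjustment.

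**The case against.** The strongest defence is that SAP 6 already covers everything: it requires every outcome to be described, and applies its tests to primary and secondary outcomes alike. For a percentage this leaves Chi square or Fisher's exact test. That stands. A reader might infer that edema and neovascular glaucoma/vitreous hemorrhage will go unanalysed, or that the listed outcomes have been replaced. The documents do not support either: SAP 6.2 adds measures, and SAP 6 still reaches the listed ones. What the general text does not supply is the denominator, period and early-leaver rule.

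The openings are also narrower than they may look. Counting available subjects is a natural literal reading for edema, and the design overview describes treatment of macular edema, so Day 0 prevalence may be high and the gap small. The 104-week follow-up is a natural window for the third outcome. Both readings still need to be written down, because the edema wording points two ways and the available-case rule does not settle how an event-free early leaver counts.

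It can be said that other measures catch the missing events. Neovascular glaucoma is grade 3 of the neovascularization scale in Appendix F, and SAP 6.1 reports adverse events by cohort. But any neovascularization at a visit is not cumulative avoidance of neovascular glaucoma, retinal hemorrhage is not vitreous hemorrhage, and mean CMT is not a percentage with edema.

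On CMT, a reader might infer that raw follow-up means are invalid. They are not: randomisation makes them unbiased, and the loss is one of precision. Strictly this holds within a vision stratum, because SAP 2.1 uses different allocation ratios in the two strata; that is a separate matter. Nor is this a case about false positives, since relabelling measures does not reduce the number of tests.

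**Conclusion.** The mismatch is confirmed by the text and needs no assumption: SAP 6.2 names 1 of 3 listed secondary outcomes and calls 4 unlisted measures plus correlations secondary. The primary analysis is untouched, so this should be corrected but does not undermine the trial. The finding is that two listed outcomes lack an outcome-specific analysis, not that they lack any.

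The only efficiency figure is the 5-29% lower standard error for CMT, which rests on an assumed correlation of 0.3-0.7. The percentage shifts for edema and for neovascular glaucoma/vitreous hemorrhage rest on invented prevalences, event counts and dropout; they show that the choices matter and do not estimate by how much in this trial.

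**What to change.** Rewrite SAP 6.2 so that each SAP 4.2 outcome has its own entry.

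1. **Injections through Week 104.** Compare by cohort with a method that allows unequal variances (for example Welch), since SAP 2.1 itself expects less variability in the monthly group; keep the Bonferroni correction for pairs. State how early leavers are handled, for example by also reporting injections per time followed. Report laser (B+C) against non-laser (A) for SAP 3.2, with the caveat that Cohort C also differs from A in injection regimen, so this contrast does not isolate laser.
2. **Persistent edema at Weeks 48 and 104.** Fisher's exact test by cohort among eyes with SD-OCT edema at Day 0 and an SD-OCT at that visit, with the percentage of all available subjects beside it. Give one definition of edema for the analysis, including whether the cysts that Appendix E accepts as dry count.
3. **New neovascular glaucoma or vitreous hemorrhage, Day 0 to Week 104.** Fisher's exact test by cohort among all treated subjects, reporting how many left early without an event.

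Label CMT, the retinal signs and the correlations additional or exploratory. State which recorded thickness CMT is, and analyse it adjusted for its Day 0 value. Report baseline values descriptively, without tests between cohorts. Label secondary p-values nominal, since the stated correction covers pairwise comparisons only.

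The cost is mainly SAP wording. SD-OCT is done and thickness recorded at every visit, but the protocol does not say that edema is recorded as yes or no, so archived scans may have to be read. The main edema analysis leaves out eyes without edema at Day 0, whose number is not given. Parts of SAP 2.1 and 6 are in the past tense; if outcome data had been seen when the text is revised, mark the choice of denominator as post hoc.
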